2.3 Trial design

A randomised, double blind, placebo controlled, 3x2 factorial feasibility study comparing low dose (100mg) or standard dose (300mg) aspirin vs. placebo and/or Vitamin D3(4000 IU) vs. placebo in men electing to enter a surveillance programme for prostate cancer.

The aim is to proceed to a definitive trial if the PROVENT Data Monitoring Committee identify, after a 9 month initiation period, that study recruitment is adequate i.e. average of 6 patients recruited per

month, and that data monitoring of 50% of the feasibility group shows minimal adverse effects in any of the arms of the trial. This will also depend on funding being secured for the main trial.

2.4 Trial Scheme Diagram

* If deemed appropriate by treating physician

3.0 Subject Selection

3.1 Number of Subjects and Subject Selection

This feasibility study aims to randomise 102 men within a period of twelve months. The study population is male patients over 16 years of age, who have been diagnosed with prostate cancer, have an estimated life expectancy of more than three years, and who have opted for Active Surveillance as their preferred prostate cancer therapy.

Participants must fulfil the inclusion and exclusion criteria. All patients who meet the eligibility criteria and are randomised will be included in the intention to treat (ITT) analysis.

17 men will be randomised into each of the six study arms in a 3 x 2 factorial design with a 1:1:1:1:1 ratio. In order to maintain treatment blinding, placebo aspirin will be size matched with the active treatment, and given as either a small (100mg) size or standard (300mg) size.

3.2 Inclusion Criteria

- 1. Male subjects aged 16 years or over with an estimated life expectancy of more than 3 years
- 2. Willing and able to provide written informed consent
- 3. Serum calcium (corrected) ≤2.65mmol/l
- 4. No previous treatment for prostate cancer (including surgery, hormone therapy, radiotherapy, cryotherapy)
- 5. All subjects must have undergone Magnetic Resonance Imaging (MRI) of the prostate with targeted biopsy of any identified lesions in addition to standard systematic biopsy.
- 6. Histologically confirmed prostate cancer following prostate biopsy including at least 10 cores of prostate tissue, in men opting for Active Surveillance as their primary cancer therapy.

Biopsies should be at least a 10-core systematic ultrasound guided prostate biopsy. For the majority of men the route of biopsy is likely to be transrectal, although the perineal route is not a contraindication to study participation. Targeted biopsies may be performed via the transrectal or perineal route. Men are eligible for the PROVENT study providing concordance exists between the location of MRI detected lesion and the location of positive biopsy core. If no concordance exists, a further prostate biopsy with lesion targeting will be required prior to randomisation, and histological analysis must fulfil study definition as a low to intermediate risk prostate cancer.

Targeted biopsies of MRI lesions must be sent in a separate pot/s from systematic biopsies and be clearly labelled. A minimum of two targeted biopsies per MRI detected lesion is required.

At 12 months, all men will be required to undergo repeat prostate biopsy. Again, the route of biopsy, transrectal or perineal, is not mandated. Patients must have systematic and targeted biopsies at the 12-month point using the same methods as described at study entry.

All patients included in the study should be enrolled in an Active Surveillance management programme for prostate cancer. Patients may be included if they have Gleason 6 or 7, (Gleason 3+3 or 3+4), organ confined disease, with a PSA of 15.0 ng/ml or less, and have a clinical and radiological stage of less than T3. The largest cancer core length should be less than 10mm.

Patients must have undergone a multi-parametric MRI deemed assessable by the study radiologist, and any lesions seen must have undergone targeted biopsy (transrectal or transperineal) within 12 months of study registration.

3.3 Exclusion criteria

- 1. Previously treated prostate cancer (including radiotherapy, hormone therapy, brachytherapy or surgery).
- 2. Currently enrolled, or has been a participant within the last 30 days, in any other investigational drug or device study.
- 3. Current, daily use of aspirin or NSAIDs, or daily dietary supplements/medication containing more than 400 IU (10 micrograms per day) of Vitamin D3; or chronic use (defined as >6 months continuous daily use) of either aspirin or replacement Vitamin D3 within two years of study enrolment (Paracetamol will be recommended where aspirin or NSAID might normally be used for pain or fever)

- 4. Current or previous use of $5-\alpha$ reductase inhibitors such as finasteride or dutasteride
- 5. Not willing to comply with the procedural requirements of this protocol including repeat prostate biopsies
- 6. Known allergy/sensitivity to, or intolerance of, acetylsalicylic acid, other salicylates or NSAIDs e.g. ibuprofen/naproxen
- 7. Previous history of gastro-intestinal bleeding or peptic ulceration, severe dyspepsia or inflammatory bowel disease
- 8. Haemophilia or other bleeding diatheses
- 9. Prior history of renal stone disease
- 10. Chronic kidney disease (≥stage 4)
- 11. Known hypercalcaemia (serum calcium >2.65 mmol/l) or untreated/uncontrolled hyperparathyroidism
- 12. Any bowel condition that would make repeat transrectal biopsy hazardous or difficult to perform e.g. recto-urethral fistula, or prior bowel surgery such as abdomino-perineal resection.
- 13. Any malignancy (other than non-melanoma skin cancer) that has not been in complete remission for five years
- 14. Any serious co-existent medical condition that would make repeat prostate biopsy hazardous e.g. anti-coagulation requiring continuous administration.
- 15. Severe Asthma
- 16. G6PD deficiency
- 17. Pre-existing macular degeneration
- 18. All contraindications to aspirin and Vitamin D3, including concomitant therapy with any medication that may interact with aspirin or Vitamin D3 as listed in section 4.10
- 19. Regular consumption of alcohol units greater than the recommended daily limit of 3-4 units per day (men)

3.4 Criteria for treatment discontinuation and early withdrawal

Treatment discontinuation

One year following study entry, patients will undergo disease reclassification to identify cancers that have progressed over the 12-month period. Disease reclassification will include repeat MRI of the prostate, together with repeat systematic and targeted prostate biopsy. Any patient whose cancer has progressed as defined in section 1.1, may continue on the study, providing they;

- are still deemed suitable for continued surveillance by their treating clinician
- do not undergo radical therapy &
- are authorised to do so by the Principal Investigator at that centre.

The reason for continuing on Active surveillance should be documented on the eCRF.

Patients undergoing radical therapy will discontinue study medication and an End of Study eCRF will be completed. No more study follow-up appointments will take place. The decision to proceed with radical therapy will be at the clinician's and patient's discretion. Unless explicitly requested in writing, by the

participant, data collected up to the 'End of Study' date will remain part of the trial. This will usually include the 12mth samples & eCRFs, as in most cases, these will have already been collected by the time the results of the disease reclassification are available.

Where a radical prostatectomy is carried out, every effort will be made to obtain pathological data and/or tissue, providing it can be acquired before the participant attends their PROVENT End of Study appointment. It is estimated that up to 30% of men will be identified to have disease progression upon disease reclassification.

Where progression is found and/or the decision is made to undergo radical therapy after 12 months but before 18 months, the participant will be required to leave the trial. An End of Study form must be completed, \geq 30 days after the participant took their last dose of IMP, for post treatment pharmacovigilance. Samples that would normally have been obtained at the 18 month follow-up appointment, will be collected wherever possible.

Early withdrawal

Patients may withdraw from the trial at any time at their own request or they may be withdrawn at any time at the discretion of the investigator if it is considered to be in the best interest of the patient. Patients can withdraw without giving a reason, but if a reason is given this should be documented in the eCRF and medical notes. It is possible for a patient to withdraw from treatment but continue to be followed up via eCRF, in clinic or by telephone. A 'Withdrawal from Treatment' eCRF will be completed. If patients do not wish to continue in this way, an 'End of Study' eCRF will be completed and they will not have any further visits.

The main analyses will be by intention to treat, therefore, data and samples collected up to the time of withdrawal of consent will be included in the study analyses, as stated in the consent form. Such data or samples will be included in the analysis, unless explicitly forbidden, again, in writing by the participant.

Patients may be withdrawn from trial medication, and/or the study in the event of:

- Unacceptable toxicity/intolerable side effects
- Inter-current illness
- Patient withdrawing consent
- Patient unable to comply with the study schedule
- Interruption of study drug intake for greater than 60 days
- Patient chooses to come off Active Surveillance and undergo active therapy
- Rise in serum calcium above upper limit of normal or 2.65mmol/l
- Identification of higher risk disease unsuitable for surveillance following 'For Cause' repeat prostate biopsy precipitated by an increasing PSA
- Development of new dyspeptic symptoms, or any sign of gastro-intestinal bleeding (haematemesis, melaena, decreased haemoglobin)
- Any episode of haemorrhage or development of a bleeding disorder
- Development of a condition not compatible with the study, or the addition of a new incompatible medication e.g. NSAID, or other product as in section 4.10
- Disease progression

Data concerning toxicity will be collected using the diary cards issued to all participants, which will allow symptoms to be classified as mild, moderate or severe. Data will also be collected on the Case Report Forms regarding gastro-intestinal bleeding and hypercalcaemia. Blood calcium levels will be monitored six monthly and any emergency hospital admissions reported, in which hypercalcaemia is identified, will be documented and followed up by the research team.

Patients who interrupt study drug intake for a cumulative total of greater than 60 days, in a 3 month period between follow-up appointments, will be considered as non-compliant and will be discontinued from the study. An 'End of Study, eCRF will be completed, and no further follow-up appointments conducted. These patients will be included in the intention to treat and safety analyses. They will be included in the efficacy assessment only if they have received at least three 90 day cycles of treatment.

Patients will be considered to be lost to follow-up if there has been as no contact for ≥6 months from the last scheduled clinic visit. These patients will be included in the intention to treat and safety analyses. They will be included in the efficacy assessment only if they have received at least three 90 day cycles of treatment.

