1.5 Risks/Benefits

Up to half of men with low to intermediate risk prostate cancer entered into an Active Surveillance programme experience prostate cancer progression within three to five years of diagnosis. Disease progression often results in the recommendation that the patient undergo radical therapy with its associated toxicity. Furthermore, historic data demonstrate that between 40 - 60% of men with low to intermediate risk prostate cancer in the UK (up to 90% in the USA) have received radical therapy for their disease. Many of these men will have chosen radical therapy due to the possibility of prostate cancer progression on Active Surveillance.

The main objective of this initial randomised feasibility trial is to demonstrate power of recruitment and the potential numbers required for a definitive protocol. The potential will be identified through the disease progression rate (histological or biological). The standard of care for men entering an Active Surveillance programme is careful disease monitoring, including serial serum PSA analysis and repeat prostate biopsies, together with repeat prostate imaging. In the PROVENT feasibility study, low dose (100mg) or standard dose (300mg) aspirin and/or Vitamin D3 compared to placebo will be evaluated in men enrolled into an Active Surveillance programme for prostate cancer. Although both Aspirin and Vitamin D3 have known toxicities, (see section 1.2 and 1.3, both are generally well tolerated. As such, we believe that for men on surveillance, the benefits of taking these agents to prevent prostate cancer progression would outweigh the side effects caused by the medication.

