5.1 Informed Consent Procedures

Potentially eligible patients who have been recently diagnosed with prostate cancer will be identified by the clinical team in the outpatient clinic, having undergone MRI scanning and systematic and/or targeted prostate biopsy. In addition, patients already managed by Active Surveillance may be eligible for PROVENT providing they have undergone disease reclassification (prostate biopsy plus MRI imaging) within the previous 12 months. These patients will be identified in the follow up clinic by the clinical staff.

The clinical care team at each site will be responsible for informing the patient of his diagnosis and discussing the available treatment options, including (if appropriate) Active Surveillance. Patients for whom Active Surveillance is a treatment option will be assessed by a clinician for study eligibility and, if suitable, will be given a Patient Information Sheet (PIS) explaining the PROVENT study. This will be documented in the patient's notes.

The Investigator will discuss the study with the patient, and, if interested, the Investigator or a trained member of the research team will explain the study in more detail. The patient's details will be added to the locally held Pre-screening Log, using only his initials and day (dd, 1 to 31) of birth as identifiers. The patient will then be given a further appointment to return and discuss their preferred treatment with the Investigator as per normal practice, giving at least 24 hours to consider his treatment options and read the PIS.

The Principal Investigator is responsible for ensuring that participants are fully aware and understand all the requirements expected of them. If the Investigator has concerns about a patient's understanding of the trial and PIS, and/or of their ability to adhere to the protocol requirements, the patient will not be entered into the trial.

At the follow up appointment, the clinician/Investigator will discuss the patient's choice of treatment, and, if his preferred option is Active Surveillance, his interest in the trial will be established. Should he wish to take part in the research written informed consent will be obtained before proceeding further and he will receive a pre-randomisation ID,

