5.4 Visit Schedule

Initial screening in routine clinic

Patients will normally attend a routine clinic to learn their diagnosis and treatment options. Those men identified as suitable candidates for Active Surveillance, and who appear to fulfil the inclusion criteria for the study, will be informed about the PROVENT study as an option within Active Surveillance. The clinic doctor will explain the study to the patient and a Patient Information Sheet will be given to him to take home for consideration. A follow up appointment will be arranged for him to return to confirm his treatment preference, and his initials and day (dd) of birth will be recorded on the locally held Prescreening Log.

Consent Visit

If, at the follow up appointment, the patient expresses a wish to take part in the study, the Investigator or Research Nurse will explain the aims, methods, anticipated benefits and potential hazards of the trial, ensure they have been fully understood and allow the patient the opportunity to ask questions. If the patient is still willing to take part, he will be given a pre-randomisation registration ID. This will be generated within the PROVENT application using the patient's initials and day, (DD), of birth. The consent form will be completed and signed as previously described, & the Eligibility Assessment eCRF will be completed using the pre- randomisation ID for reference.

Serum Calcium Testing

An existing serum calcium result will be acceptable if taken within 2 months prior to the Eligibility Assessment date. Alternatively, once consent has been obtained, a blood sample will be taken to confirm serum calcium is within the acceptable range for participation in the study. The result will be obtained prior to the randomisation visit and, if above the accepted range, the patient and his GP will be informed of the result and the randomisation visit cancelled.

PSA Testing

An existing PSA result will be acceptable if taken within 3 months prior to the Eligibility Assessment date. Alternatively, once consent has been obtained, a blood sample will be taken to confirm the PSA level is within the acceptable range for participation in the study. The result will be obtained prior to the randomisation visit and, if above the accepted range, the patient and his GP will be informed of the result and the randomisation visit cancelled.

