Repeat biopsies may occur from week 48 to week 56 depending on clinic waiting times; therefore study medication may be taken for up to four weeks more, or less, than 12 months in the weeks leading up to the routine biopsy.

Patients will undergo biopsy with prophylactic antibiotic administration as per normal procedures. This may be either a TRUS biopsy or a template biopsy and performed under local anaesthesia or general

anaesthesia using a 12 Hz ultrasound probe. The procedure will comprise a standard systematic biopsy together with targeted biopsies taken from any MRI detected abnormalities.

Biopsy cores should be sent to local laboratories separately from each region of the prostate, with no more than two cores per pot, and labelled according to the region of the prostate sampled. In patients with MRI detected prostate lesions, at least one targeted biopsy core should be directed to each lesion and placed in a separately labelled pot. Tissue taken will be processed locally as per the PROVENT Laboratory Manual.

If clinically necessary, repeat biopsy can be brought forward, or not performed, at the discretion of the Investigator. Alternatively, a patient may decide to leave the trial and undergo radical prostate cancer therapy during the 18-month study period; however the case should be presented at a multidisciplinary team meeting before an alternative management strategy is commenced. Patients who undergo radical treatment will stop trial medication at this point and not be followed up. Patients remaining on Active Surveillance but not undergoing a repeat biopsy will remain in the study for analysis as PSA dynamics over the study period will still be available.

Abnormal laboratory test results

A laboratory abnormality in one of the study specific tests, such as serum corrected calcium or H Pylori, may require the subject to undergo treatment. A value flagged, for example, as 'clinically significant' must be entered on the Adverse Event CRF. In addition, the test may need to be repeated at the Investigator's discretion. The Investigator may use his/her own judgment as to whether the abnormal finding is sufficient reason to immediately withdraw the patient from the study.

Any laboratory value that meets the definition of Serious Adverse Event must be reported as an SAE (refer to 7.1.3). In addition, the patient should be reassessed for continuation in the study and any indicated and appropriate therapies should be initiated.

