5.8 Radiology Assessments

Patients will undergo Magnetic Resonance Imaging (MRI) prior to entry and at 12 months as part of their routine treatment on Active Surveillance.

Progression of prostate cancer will be defined as the development of a lesion on multi-parametric imaging where no MRI lesion was identified on the screening MRI, or alternatively, an MRI scan that demonstrates that a lesion identified on screening MRI has increased in volume over the study period by greater than 33%.

Patients will undergo multi-parametric MRI imaging of the prostate. The scan will be performed & reported using each site's routine practice and locally defined parameters. The details of the procedure & the results will be recorded on a 'MRI Procedure & Results' eCRF. In addition, a pseudo-anonymised copy of the report will be uploaded to the PROVENT application.

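### MRI and histological progression are measured from a reference examination that may be 12 months old at registration, so the interval is about 11 to 25 months rather than the stated 12

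*Protocol*

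**What the plan says.** **The period claimed.** Section 3.4 says that one year after entry "patients will undergo disease reclassification to identify cancers that have progressed over the 12-month period". Section 5.8 defines MRI progression partly by whether "a lesion identified on screening MRI has increased in volume over the study period" beyond a threshold of 33%.

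**The reference examination.** Section 3.2 requires an assessable multi-parametric MRI and says that "any lesions seen must have undergone targeted biopsy (transrectal or transperineal) within 12 months of study registration". Section 5.1 admits men already on surveillance "providing they have undergone disease reclassification (prostate biopsy plus MRI imaging) within the previous 12 months". The schedule in 5.5 has MRI and biopsy before the study and at 12 months only. Its validity footnote sets limits for calcium (2 months) and PSA (3 months). Section 3.2 asks for a further biopsy before randomisation only when the MRI lesion and the positive core do not match. Sections 1.1, 2.2, 5.8 and 8.2 all judge MRI change against the screening scan. Histological change is judged at the repeat biopsy, for which the routine comparator is the pre-entry biopsy.

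**The reassessment.** Section 5.4: "Repeat biopsies may occur from week 48 to week 56 depending on clinic waiting times". Section 5.8 gives the repeat MRI simply as at 12 months. Study drug is first issued at randomisation (4.5).

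**PSA.** Section 5.4: "An existing PSA result will be acceptable if taken within 3 months prior to the Eligibility Assessment date". Biochemical progression is a 50% rise from baseline at 12 months. Section 5.5 lists no PSA at the randomisation visit, and Appendix 1 lists one there only if the window has lapsed.

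**Use of the result.** Section 8.2 summarises MRI and PSA progression as a share of all study men. On the numbers for the definitive trial, section 1.5 says: "The potential will be identified through the disease progression rate (histological or biological".

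**The concern.** The protocol names one interval and measures another. A man whose reference MRI and biopsy were done just before entry is observed for about a year, nearly all of it on study drug. A man staged 12 months before registration is observed for about two years, roughly half of it before any drug. Both are counted the same way in one proportion.

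Two things are at stake. First, a proportion over mixed intervals is not a 12-month rate. If it is carried into planning as one, it will tend to be too high. Second, growth before the first dose counts as progression in every arm, which tends to dilute any drug effect on MRI or histology. PSA has the same weakness on a smaller scale, because the protocol does not name the baseline value and schedules no routine PSA at randomisation.

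**Working it through.** **Inputs from the protocol**
- Age of the reference examination at registration: 0 to 12 months (3.2, 5.1).
- Randomisation to repeat biopsy: 48 to 56 weeks (5.4).
- Registration to randomisation: no limit found, so taken as 0.
- Progression expected at reclassification: up to 30% (3.4).

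**The stated 12 months.** This is reproduced only if the reference examination is done at entry and reassessment falls exactly at one year: 0 + 12 = 12 months.

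**The actual range.** One month is 365.25/12 = 30.44 days.
- 48 weeks = 336/30.44 = 11.0 months; 56 weeks = 392/30.44 = 12.9 months.
- Shortest interval: 0 + 11.0 = 11.0 months.
- Longest interval: 12 + 12.9 = 24.9 months.
- Largest share before the first dose: 12/24.9 = 48% at week 56, and 12/(12 + 11.0) = 52% at week 48.
- An assumed 1 to 2 months from registration to randomisation moves the upper end to 25.9 to 26.9 months.

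Four qualifications apply to this range:
- The week 48 to 56 window is stated for biopsy. If the repeat MRI is at exactly 12 months, its range is 12 to 24 months.
- In 3.2 the 12-month limit can be read as attaching to the targeted biopsy alone. MRI age in newly diagnosed men would then have no limit, and the upper end would be higher.
- Section 5.4 lets the biopsy be brought forward, so the lower end can fall below 11 months.
- PSA, measured from a result up to 3 months before the eligibility assessment, spans about 12 to 15 months.

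**What the interval does to a proportion (illustration only).** Assume a constant hazard giving 30% in 12 months. The risk over T months is 1 − 0.70^(T/12).
- T = 11.0: 28%
- T = 12: 30%
- T = 18: 41%
- T = 24.9: 52%

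Read the other way, if 30% is what is seen at an interval of 18 months, the 12-month risk is 1 − 0.70^(12/18) = 21%.

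**What it does to the volume threshold.** A 33% increase corresponds to annual growth of 1.33^(12/11.0) − 1 = 36% over the shortest interval, and 1.33^(12/24.9) − 1 = 15% over the longest.

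**Why crude events per person-year is not the repair.** Progression is seen only at reassessment, so its date is unknown. Take the same hazard, −ln 0.70 = 0.357 per year, with a lag L spread evenly over 0 to 1 year (an assumption) and reassessment at one year.
- Expected proportion: the mean of 1 − 0.70^(1+L) = 1 − 0.70 × 0.30/0.357 = 0.411.
- Mean interval: 1.5 years.
- Crude rate: 0.411/1.5 = 0.274 per year, against the true 0.357.
- Implied 12-month risk: 1 − exp(−0.274) = 24%, against 30%.

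**The case against.** **Consequence.** This is a feasibility study with recruitment as its primary endpoint, and nothing here touches that. Section 8.2 describes MRI and PSA progression, and the only test named for secondary endpoints in 8.5 is a stratified Wilcoxon on assay values. No powered progression comparison exists to be damaged. This stands, and it limits the weight of the point.

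**Bias between arms.** A reader might infer that the treatment comparison is biased. The documents do not support that: randomisation balances the lag on average. What remains is some dilution, plus chance imbalance with 17 men per arm.

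**Size.** A reader might infer that the observed proportion will be 41% or more, or put a figure on the dilution of a drug effect. Neither can be drawn from the protocol. Its figure of up to 30% is an upper bound for what reclassification will find as actually performed, not a 12-month risk from a fresh biopsy. The lag distribution is not given. Sections 5.1 and 5.4 mainly describe recently diagnosed men, so lags may cluster short. If apparent progression is largely biopsy sampling error, interval length matters less.

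**Planning.** A reader might infer that the figure of 800 is undermined. Section 8.4 already states 800 and uses the feasibility data to set the number of centres. If the definitive trial keeps the same entry window and reference examinations, the crude proportion at reassessment is the relevant planning quantity. Even so, 1.5 does say that the progression rate will inform the numbers.

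**The analysis plan.** Adjustment and estimation are commonly left to it, and it is not shown, so their absence is not the finding. What stands is the interval wrongly described in 3.4 and 5.8, and a PSA sampling schedule that no analysis plan can change afterwards.

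**Conclusion.** The point stands as an error of definition with limited consequences. On the protocol's own windows, MRI and histological progression span about 11 to 25 months, and up to about half of that can precede the first dose. The 12-month description in 3.4 and the study-period description in 5.8 are wrong for any man not examined close to entry. The crude proportion should not be used as a 12-month on-study rate under 1.5.

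The range of the interval follows from the documents, given no delay from registration to randomisation and the reading that the 12-month limit covers both MRI and biopsy. How far the proportion is distorted does not follow from them. The figures of 28%, 41% and 52% rest on an assumed constant hazard and on taking 30% as a 12-month risk. The primary endpoint is unaffected. The change is worth making because it is cheap and because the progression rate is meant to inform the next trial.

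**What to change.** Keep the entry window, so that recruitment is not affected.

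1. Reword 3.4, 5.8 and 8.2 so that MRI and histological progression is counted since the reference (screening) MRI or biopsy. Beside each proportion, report the distribution of the reference-to-randomisation and reference-to-reassessment intervals.
2. In any active-versus-placebo comparison of MRI or histological progression, include time from reference examination to randomisation as a covariate.
3. If a 12-month rate is carried into planning, estimate it with a current-status method, for example a complementary log-log model with the log of the interval as offset. Do not use the crude proportion or crude events per person-year. The exception is a definitive trial that keeps the same entry window and reference examination, where the crude proportion applies directly. The offset assumes a constant hazard; a free coefficient on log interval would relax that.
4. Take PSA with the randomisation bloods in all men and name it as the baseline for the 50% rise. Keep the 3-month window for eligibility only.

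Items 2 and 3 can sit in the statistical analysis plan if they are not already there. The cost is revised wording, a little more analysis, and one PSA tube at a visit where section 5.4 already has blood drawn for androgens and vitamin D. The stated 12-month progression rate may come out lower.
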